2. Secondary (comparison of each listed parameter between the prospective treatment groups in addition to comparison of each treatment group with historic controls):
 - a. Growth (rate of change)

- i. Weight, length, and head circumference at enrollment, on a weekly basis while receiving study lipid, and 2-3 weeks post-study lipid completion.
- ii. Weight, length, and head circumference at 36 weeks corrected gestational age and time of discharge.
- b. Essential fatty acid profile differences and development of deficiency
- c. Average total caloric intake for all patients on weekly basis
 - i. Average lipid dose delivered on weekly basis
- d. Feeding tolerance/ percentage of total calories from enteral feeds
 - i. Time to achievement of enteral autonomy (full enteral feedings)
 - ii. Percentage of enteral calories at end of study
 - iii. Percentage of patients in each group with enteral autonomy
- e. Transaminase, alkaline phosphatase, GGT levels at enrollment, every 4 week time point, and end of study
- f. Triglyceride concentration at baseline, weekly, and end of study
- g. Rates of other diagnoses in each study group
 - i. Retinopathy of prematurity as diagnosed by Ophthalmologic examination
 - ii. Chronic lung disease as defined by need for oxygen at time of discharge or 36 weeks corrected gestational age (if at least 28 days of age), whichever comes first.
- h. Rates of adverse and serious adverse events in each group
- i. Length of stay
- j. Two year neurodevelopmental differences using ASQ-3 screening

Study Population

Inclusion criteria

Infants admitted to the Riley Hospital Neonatal Intensive Care Unit (NICU), regardless of postmenstrual or corrected gestational age, with anticipated need for parenteral nutrition for four or more weeks PLUS one or more of the additional inclusion criteria listed below will be eligible for inclusion within the study and for randomization. Inclusion criteria include:

- Anatomic intestinal defect: Neonate with intestinal atresia, omphalocele, gastroschisis or volvulus with or without intestinal resection and need for parenteral nutrition pre or post-operatively.
- Ischemic/perforation intestinal injury: Neonates with spontaneous intestinal perforation or necrotizing enterocolitis requiring surgical intervention with need for parenteral nutrition post-operatively.

Exclusion criteria at time of study enrollment

- Infant with current weight less than 750 grams

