A group of 24 patients previously treated in the Riley NICU from the years 2016 – 2017 will be used as a historic control cohort. Historic patients will be eligible for enrollment in the study if they have one of the above listed diagnoses, received post-operative parenteral nutrition, and were treated with soy-based lipid at standard dosing (2-3 g/kg/day). Historic patients will be ineligible to participate if any of the above listed exclusion criteria are true at the time of their abdominal surgery. Historic patients will be matched to prospective patients when able. This matching will first utilize in order: 1. days of parenteral lipid therapy, 2. diagnosis, 3. birth gestational age, and 4. birth weight when selecting for inclusion.

Study Procedures

1. Smoflipid® (20% lipid emulsion) treatment group
 - a. Advancement:
 - i. Smoflipid will be started at 1 g/kg/d on day 1 of parenteral nutrition after enrollment and advanced by 1 g/kg/d each subsequent day to a goal maximum of 3 g/kg/d
 - b. Maintenance and weaning [8]:
 - i. The Table below will be used as a guide for weaning Smoflipid as enteral nutrition is initiated and advanced.
 - ii. Patients will continue to be monitored by a clinical dietitian and pharmacist as per standard of care. Pending their recommendations, along with the clinical state of the child, the actual dose of Smoflipid needed may vary by individual patient.
 - c. Other parenteral nutrition components
 - i. Amino acid will be provided to meet estimated protein requirements only and will not be increased as a form of caloric intake.
 1. Term infant approximate goal of 3 g/kg/day and preterm infant approximate goal of 3.5 – 4 g/kg/day.
 - ii. Glucose infusion will be utilized and advanced per standard protocol to provide remainder of estimated non-protein caloric need of each individual patient.
 1. Maximum glucose infusion rate (GIR) while enrolled in study of 16 mg/kg/min. If further caloric intake is required, Smoflipid will be increased to a maximum of 3 g/kg/d.

Table 1: Smoflipid dosage recommendations for weaning as enteral feeds advanced

% calories from PN	Volume enteral feeds (ml/kg/d)	Enteral calories (kcal/kg/d)	Lipid (g/kg/d)
80-100%	\leq 20-40	\leq 30	3
60-80%	40-60	30-40	3
50-60%	60-80	40-50	2.5
40-50%	80-100	50-60	2
30-40%	100-110	60-70	1.5
20-30%	120	70-90	1
<20%	>120	>90	0

2. Intralipid® (20% lipid emulsion) reduction treatment group
 - a. Advancement:
 - i. Intralipid:

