- iv. Subjects leaving the study secondary to parental request may not have further follow-up performed if at the request of the parent.

Historic Controls

Historic controls will have their charts reviewed to document the same information as for prospective patients. For historic controls, this information will be limited to their time admitted to Riley Hospital only. Information recorded will include:

- 1. Diagnosis and procedures:
 - a. Documentation of diagnosis making eligible for study participation
 - b. Documentation of surgery performed
- 2. Parenteral nutrition:
 - a. Length of parenteral nutrition: Documentation of total days of parenteral nutrition including start date, stop date, and dates not receiving parenteral nutrition.
 - b. Lipid dosing: maximum lipid dose, average lipid dose on weekly basis
 - c. Glucose dosing: documentation of glucose infusion rate (GIR) including maximum dose and weekly average GIR dose
 - d. Protein dosing: documentation of maximum amino acid dose received and weekly average amino acid dose
 - e. Discontinuation of parenteral nutrition: including reason for discontinuing and for what length of time.
- 3. Enteral Feeding:
 - a. Autonomy: the time from start of enteral feeding until complete enteral autonomy (enteral feeding only) will be documented for each patient.
 - b. Weekly enteral feeding: On a weekly basis an average of enteral feeding intake will be determined both in volume and calories. Based on these calculations a percentage of overall intake related to parenteral nutrition will be determined.

- c. Milk intake: The particular milk prescribed to each patient will be documented along with the particular form of additives and fortification used.
- 4. Measurements:
 - a. Weight, length, and head circumference will be recorded on a weekly basis for each patient.
 - b. Corrected measurements will also be obtained for each patient at 36 weeks corrected gestational age and the time of discharge from the Riley NICU. Given these are historic patients, the values obtain closest to these dates will be used for the purposes of this study.
- 5. Laboratory values:
 - a. Laboratory values listed above for prospective patients will be documented for historic patients if available within the electronic medical record.
 - b. If cholestasis is diagnosed the interventions and treatments received by the patients will be documented.
- 6. Diagnoses of prematurity

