- ii) In adequate patient recruitment. We anticipate recruiting an average of 4 patients per study month. If there is a significant lag and will be unable to obtain our full number of patients within a reasonable time, this will be reason to terminate the study early.
- b) Principle investigators will consider study cessation if SAEs occur within a specific treatment arm out of proportion to what would be expected from typical disease course.

Statistical Considerations

Our goal is to recruit 25 patients into each group. Given this is a pilot study, the minimum number needed per arm would be 12 patients as per published statistician recommendations [21]. The reasoning for using a pilot study include determining the feasibility of performing a larger scale study. Performing a pilot study prior to the large-scale study will give us information on patient recruitment and retention, along with design flaws that may be remedied prior to future studies.

All data will be summarized by group at each time point; summaries will include frequencies and proportions for categorical variables and mean, standard deviation, and range for continuous variables. Distributions of continuous variables will be examined. Parenteral nutrition characteristics will be recorded and tabulated. Tabulated categorical outcomes will include: proportions of subjects with cholestasis or IFALD, essential fatty acid deficiency, enteral autonomy at end of study, retinopathy of prematurity, chronic lung disease, and adverse events. Tabulated continuous measurements will include: growth rates, essential fatty acid profile, total caloric intake, percentage of calories from enteral intake, time to enteral autonomy, lipid dose delivered, bilirubin level, liver enzymes, gamma-glutamyl transferase (GGT), triglycerides, and length of stay. Fisher's Exact Tests will be used to compare between groups for categorical variables. Time to enteral autonomy will be evaluated using Kaplan-Meier survival curves and a log-rank test. Mixed models will be used to compare between groups and compare within groups over time for continuous variables measured throughout the study. Length of stay will be compared using a Wilcoxon Rank Sum test. A 5% significance level will be used for all tests mentioned.

Privacy/Confidentiality Issues

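### The only written clock for time to enteral autonomy starts at first enteral feed, not at randomisation or a named control index date

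*Combined protocol and SAP*

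**What the plan says.** Study Objectives, item 2.d.i, lists the endpoint as "Time to achievement of enteral autonomy (full enteral feedings" with no starting point. The lead-in to the secondary objectives plans "comparison of each listed parameter between the prospective treatment groups in addition to comparison of each treatment group with historic controls", so the endpoint is compared both between the arms and with controls.

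Statistical Considerations gives the method: "Time to enteral autonomy will be evaluated using Kaplan-Meier survival curves and a log-rank test". It adds that "A 5% significance level will be used for all tests mentioned". It gives no origin, no censoring or delayed-entry rule, and no rule for infants who are never fed.

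The one place that defines the interval is the data list for historic controls (Historic Controls, item 3.a): "the time from start of enteral feeding until complete enteral autonomy (enteral feeding only) will be documented for each patient". That list opens with "Historic controls will have their charts reviewed to document the same information as for prospective patients".

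Two other passages bear on when first feed can occur. Inclusion criteria admit infants "regardless of postmenstrual or corrected gestational age, with anticipated need for parenteral nutrition for four or more weeks", with no limit on earlier enteral feeding and no window from surgery. Study Procedures, item 1.b, says "The Table below will be used as a guide for weaning Smoflipid as enteral nutrition is initiated and advanced", so feeds may also begin while study lipid is running.

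**The concern.** A log-rank comparison of randomised groups is most secure when each infant's clock starts at randomisation, because nothing that happens afterwards can then decide who is at risk or from when. First feed is not such a point.

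- **First feed after randomisation.** Time zero is then set by clinical course and clinician choice. The trial is unblinded (Enrollment/Randomization), feed advancement follows physician practice (Study Procedures, item 3.a), and no date for first feed is scheduled. If a lipid strategy changed when feeds begin, the analysis would not show it.
- **Never fed.** Such an infant has no time zero and may be lost from the Kaplan-Meier analysis, although this is among the least favourable outcomes.
- **First feed before enrolment.** This is plausible for infants with necrotizing enterocolitis or perforation. An infant who enters still needs parenteral nutrition, so the autonomy being counted lies after enrolment and the earlier fed days are event-free by design. If trial infants and controls differ in how many such days they carry, their curves separate for a reason unrelated to lipid.

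The control comparison has a further asymmetry. Control data are limited to the stay at the study hospital, so feeds begun elsewhere may be missed and the clock started late.

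**Working it through.** The plan states no median, event count, effect size or power for this endpoint, so there is no figure to reproduce. The check has two parts.

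**1. What each clock measures.** Let R be randomisation (or the control index date), F first feed and A autonomy.

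- If F is after R: A − R = (F − R) + (A − F). The first-feed clock keeps only the last term, so any effect on F − R disappears. If F never occurs, A − F is undefined, whereas the infant is simply censored on the clock from R.
- If F is before R: A − F = (R − F) + (A − R). The term R − F contains no event. Between randomised arms its distribution is the same in expectation. Against unrandomised controls it need not be.

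**2. Illustration of size.** From the documents: 25 infants per arm, 24 controls, a 5% level (taken as two-sided, |z| > 1.96), and 84 days, the maximum time on study lipid. Using 84 days as follow-up is an assumption, because the plan sets no window for autonomy. Also assumed:

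- half the infants are fed before R, by a uniformly distributed number of days (mean 10 unless shown);
- the rest start feeds after an exponential delay from R (mean 14 days unless shown);
- autonomy follows exponentially, mean 35 days, from the later of F and R;
- infants unfed by day 84 are dropped from the first-feed analysis only.

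There were 2,000 simulated trials per row. The simulation error near 5% is √(0.05 × 0.95 / 2000) = 0.5 percentage points.

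| Scenario | Rejects, clock from R | Rejects, clock from first feed |
|---|---|---|
| Two arms, same feeding history, no effect | 5.5% | 5.4% |
| Arm vs controls, no effect; mean feeding before R 10 vs about 0 days | 5.1% | 9.6% |
| Same, 20 vs about 0 days | 5.1% | 17.2% |
| Two arms; mean delay to first feed 14 vs 35 days | 14.0% | 5.0% |
| Two arms; mean delay 14 vs 60 days | 31.2% | 4.8% |

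In the last two rows, 2.4% and 6.2% of infants had no first feed by day 84. This agrees with direct calculation. The unfed share in an arm is 0.5 × exp(−84/mean delay): 0.1% at 14 days, 4.5% at 35 and 12.3% at 60. Averaged over two equal arms, that gives (0.1 + 4.5)/2 = 2.3% and (0.1 + 12.3)/2 = 6.2%.

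The first row shows no loss of type I error control between randomised arms. The next two show false positives against controls when feeding histories differ. The last two show a real delay in starting feeds going undetected. Even from randomisation, detection is only 14–31% at this sample size.

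**The case against.** The strongest reply is that the defining sentence is a chart-abstraction item for infants who were never randomised. Recording the same information describes data collection, not an analysis time zero, so for the randomised arms the plan is silent rather than wrong. That stands in part: extending the clock to the arms is an inference. But it is the natural reading, and the alternative leaves a formally tested endpoint with no origin. The same correction is needed either way.

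A second reply is that time from first feed to full feeds is a coherent measure of feeding tolerance, the heading under which the endpoint sits. That is fair, and is a reason to keep it as a description. It does not make it a sound origin for the randomised test.

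Third, diagnosis is a stratification factor and the second matching variable for controls, which should reduce differences in feeding history. It should, but matching is only done when able, and infants with the same diagnosis can still differ in prior feeding.

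A reader might go further and infer that:

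- **the first-feed clock invalidates the comparison between arms.** Feeding before randomisation is balanced in expectation, and the simulated type I error was 5.4%.
- **never-fed infants are excluded.** No text says so; the risk comes from silence.
- **the proportion reaching autonomy is inflated.** That is a separate endpoint (item 2.d.iii) that needs no clock, and nothing removes a never-fed infant from its denominator.
- **one infant's pre-enrolment fed days, as a share of 84 days, size the bias.** That ratio measures neither a shift in the curve nor an error rate.

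**Conclusion.** The point holds in limited form. The only written origin is first enteral feed, it appears to apply to all groups, and it can fall before or after randomisation. Three consequences follow: an effect on the start of feeds would be invisible, never-fed infants have no time zero, and the comparison with historic controls is open to bias from unequal feeding before the index date.

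The size cannot be computed from the documents. The 10–17% false-positive rates against controls require an assumed difference in feeding history between cohorts. The masked effect requires an assumed influence of treatment on when feeds start. The documents supply neither, so these figures show direction and plausible scale only.

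Severity is minor to moderate. This is one secondary endpoint of a pilot, and neither the primary cholestasis endpoint nor the proportion with enteral autonomy is affected.

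**What to change.** In Statistical Considerations, define time zero for the Kaplan-Meier and log-rank analysis as randomisation in both arms and as an explicitly named, comparable index date in historic controls. Keep every infant in the risk set from that date, including those never fed. The same sentences should say how death, transfer and discharge on parenteral nutrition are handled. Report time from first feed to full feeds only as a descriptive supplement, stating which start counts when feeds stop and restart.

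The control index date has to be chosen, because none is defined for outcomes. The first Historic Controls section uses abdominal surgery only to apply the exclusion criteria. Prospective infants with anatomic defects may qualify on pre-operative parenteral nutrition, so surgery need not line up with enrolment. If surgery is chosen, report the interval from surgery to randomisation in the trial arms so that comparability can be judged.

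The cost is a few sentences and that one decision. No extra infants, visits or blood draws are needed.

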All patients will be monitored on a daily basis for the development of any adverse events (AE) from the start of the study lipid until one week (7 days) after leaving the study. An adverse event is defined as any untoward medical occurrence in a research subject temporally associated with the use of the study drug, whether or not it is related to the drug. Any worsening of a pre-existing condition or illness is considered an adverse event. This includes pre-existing and or new clinical conditions or morbidities associated with prematurity or the patient's underlying diagnoses. Laboratory abnormalities or vital sign changes are considered adverse events only if they meet the specific criteria listed in the table below. A serious adverse event (SAE) is an AE that leads to death of a subject, life-threatening event, persistent or significant disability, or an important medical event requiring medical or surgical intervention to prevent a serious outcome.

Many possible AE and SAE are listed in Table 3 below. Patients will be monitored continuously by one of the principal investigators, [name] or [name], for possible AEs and SAEs. Clinical significance and relation to the study will be determined by [name] and/or [name] based on best medical judgement. Unanticipated events that are determined to be an AE related or possibly related to the research drug will be promptly reported to the IRB by [name] or [name] within 5 business days. Major protocol issues, including drug administration issues or errors, will also be reported to the IRB within 48 hours. Events that are determined to be an SAE or lead to death of a patient will be promptly reported to the IRB within 24 hours.

A separate Data and Safety Monitoring Committee (DSMC) will be used to monitor patient outcomes and AE along with SAE events. The DSMC members will not include the primary investigation team and will be made up of other experts from Neonatology ([name]), Pediatric General Surgery ([name]), Pediatric Gastroenterology ([name]), and Statistics. The DSMC will meet within 2 weeks following enrollment of the first 10 patients. Further enrollment will be put on hold pending initial DSMC review. If no safety concerns are found by independent DSMC review, patient enrollment will proceed. DSMC will meet subsequently every 6 months for the duration of the study.

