Adverse events are defined using the Common Terminology Criteria for Adverse Events (CTCAE) version 4.0. Modifications to these definitions may be made if inappropriate for the neonatal patient population. Some specific events and definitions are listed in Table 3 below. This table does not include the CTCAE v4.0 grade 5, as this is defined as death in a patient. Therefore, any death of a patient will be defined as grade 5, irrelevant of the specific diagnostic category within CTCAE v4.0 or listed below.

Table 3: Definition of Specific Adverse and Serious Adverse Events

Event	Mild (Grade 1)	Moderate (Grade 2)	Severe (Grade 3)	Life Threatening (Grade 4)
Definition of adverse event	Mild transient symptoms only	Moderate illness or condition with	Severe illness or condition	Life threatening illness or

	monitored or symptomatic treatment. Aware of symptom but tolerated and no functional interference	new or significant altered treatment, causes some interference with normal activity or care.	unresponsive to medical treatment, incapacitating with inability to perform usual activity and interference with normal functions.	condition, required major surgery or respiratory support.
Hyperthermia (axillary temperature)	38.0-38.5 °C on single measurement	38.5-39.0 °C on single measurement	≥38.5 °C on two or more consecutive measurements	≥39.0 °C for two or more measurements despite environmental intervention or need for increased IV fluid volume
Pulmonary deterioration	Not applicable	FiO2 increase by 0.20-0.30 or new non-invasive ventilation or increase in MAP >3 during study drug infusion	FiO2 increase by 0.31-0.50 or new invasive ventilation or increase in MAP >5-7 during study drug infusion	FiO2 increase >0.50 or need for escalation in type of invasive ventilation or increase in MAP >7 during study drug infusion
Hypertension (defined as systolic blood pressure greater than the 95%ile for postmenstrual age)	Hypertension for less than a 24 hour period and no treatment needed	Hypertension 24-48 hours and no treatment needed	Hypertension for >48 hours or requiring treatment	Hypertension requiring multiple treatment types
Hyperglycemia	Transient glucose >180mg/dL for single determination with no further action taken	Glucose 180-250mg/dL for at least 2 determinations 6 hours apart	Glucose 251-350mg/dL for at least 2 determinations 6 hours apart or need for insulin or change in IV fluid	Glucose >350mg/dL, change in mental status, diuresis or dehydration

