Hypoglycemia	Transient glucose <50mg/dL on single measure	Glucose <50mg/dL on repeated measures, responds to treatment with	Glucose <40mg/dL on repeated measures or need for multiple dextrose boluses or need	Glucose <40mg/dL with change in mental status, seizures, glucose

		single intervention	for change in IV glucose infusion to >10mg/kg/min	unresponsive to glucose infusions, or need for glucagon or steroids
Elevated liver enzymes (AST and/or ALT)	1.5-2.0x normal (90-125 U/L)	2.1-4.0x normal (126-245 U/L)	4.1-10.0x normal (246-600 U/L)	>10.0x normal (>600 U/L)
Hypertriglyceridemia	150-250 mg/dL	250-500 mg/dL	500-1000 mg/dL	>1,000 mg/dL
Elevated creatinine (at >72 hours of age or older)	1.3-1.8 mg/dL	1.9-2.3 mg/dL	2.4-3.4 mg/dL	≥ 3.5mg/dL
Oliguria (urine output (UO) over 24 hour period)	UO <1.0 mL/kg/h	UO 0.5-1.0 mL/kg/h	UO <0.5 mL/kg/h	UO <0.3 mL/kg/h
Anemia (based on laboratory value)	Hct <34%	Hct <28%	Hct <24%	Hct <20% and/or cardiovascular instability from the anemia
Thrombocytopenia (platelet counts in 1000/cumm)	75-100	50-75	25-50 with no bleeding	<10 and/or bleeding
Coagulation study abnormalities	INR 1.5-2.0	INR 2.0-2.5	INR >2.5 with no clinically significant bleeding	INR >3.0 and/or >2.5 with clinically significant bleeding
Thrombosis (thrombus confirmed with imaging and radiographic report)	Non-inclusive thrombus with no associated symptoms.	Non-inclusive thrombus but with symptoms such as edema.	Thrombus leading to need for anticoagulation therapy but with no organ compromise.	Need for anti-coagulation therapy with compromise of extremity or organ related to thrombus.
Neutropenia (Absolute neutrophil count)	1600-2000	1000-1599	500-999	<500
Mental status	Mild irritability, possibly within normal range	Persistently irritable and/or intermittent lethargy	Lethargy, stupor, still arousable, single seizure	Non-responsive, need for respiratory intervention due to change

Systemic infection (including sepsis and/or bacteremia with positive blood culture)	Positive blood culture but not treated (felt to be contaminant)	Treated ≥ 5 days of consecutive antibiotics, antivirals or antifungals with no cardiovascular instability.	Treated for systemic symptoms, including cardiovascular instability and ≥ 5 days of antimicrobial with response to treatment.	Treated for systemic symptoms, including cardiovascular instability and ≥ 5 days of antimicrobial no or slow response to treatment.
---	---	---	--	--

Criteria for Stopping Study

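### Table 3 gives no grade to an isolated temperature above 39.0 °C, so it is not an adverse event although a milder single fever is; oliguria Grade 1 overlaps Grade 2, which affects grades but not counts

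*Combined protocol and SAP*

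**What the plan says.** The section on adverse events and serious adverse events restricts which measured abnormalities count: "Laboratory abnormalities or vital sign changes are considered adverse events only if they meet the specific criteria listed in the table below". The table it refers to is Table 3.

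The hyperthermia row (axillary temperature) reads:

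- Grade 1: "38.0-38.5 °C on single measurement"
- Grade 2: "38.5-39.0 °C on single measurement"
- Grade 3: "≥38.5 °C on two or more consecutive measurements"
- Grade 4: "≥39.0 °C for two or more measurements despite environmental intervention or need for increased IV fluid volume"

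The oliguria row uses one averaging window for all grades, 24 hours. Grade 1 is an output below 1.0 mL/kg/h with no lower limit, Grade 2 is "UO 0.5-1.0 mL/kg/h", Grade 3 is below 0.5 and Grade 4 is below 0.3.

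The documents give no rule for a value that meets more than one grade. Adverse event rates by group are secondary objective 2.h. Statistical Considerations lists adverse events among the tabulated categorical outcomes and compares categorical variables by Fisher's exact test. Under Criteria for Stopping Study, the monitoring committee reviews adverse events, and an excess in one group is a named safety concern.

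**The concern.** A severity scale should not lose an event as it gets worse. In the hyperthermia row the single-reading bands end at 39.0 °C, and the higher grades require repeated readings. In most tables that would only leave a grade to be queried. Here the adverse-event section makes Table 3 the test for whether a vital sign change is an adverse event at all, so an ungraded reading is also an uncounted one.

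What is at stake is the fever component of the safety comparison: the group rates under objective 2.h and the counts the monitoring committee sees. The study is unblinded and the principal investigators judge the events. A gap in the criteria therefore leaves the decision to people who know the allocation.

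The oliguria row has a different fault. Its first two grades are not distinct, so a mild category is printed that cannot be used as intended.

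**Working it through.** The plan states no figure to reproduce. The check maps values to the printed cut-points of the two rows and lists every grade each value meets.

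**Hyperthermia.** Single axillary readings from 37.9 to 40.5 °C in steps of 0.1:

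| Single reading (°C) | Grades met, no need for increased IV fluid | Grades met if that need is present and stands alone as a criterion |
|---|---|---|
| 37.9 | none | none |
| 38.0 to 38.4 | 1 | 1 |
| 38.5 | 1 and 2 | 1 and 2 |
| 38.6 to 38.9 | 2 | 2 |
| 39.0 | 2 | 2 and 4 |
| 39.1 to 40.5 | **none** | 4 |

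The last column attaches the fluid clause of Grade 4 to a reading of at least 39.0 °C and treats it as an alternative to repeated readings. If the clause is instead read as part of the repeated-reading condition, the single reading stays ungraded even when fluid is increased.

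Two readings give a different result. If the next reading is also 38.5 °C or above, the pair meets Grade 3. The gap therefore concerns isolated readings above 39.0 °C.

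**Size.** One infant in a group-specific proportion is:

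- 1/25 = 0.040, or 4 percentage points, at the target of 25 per arm
- 1/12 = 0.083, or about 8 percentage points, at the minimum of 12 per arm

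These are ceilings. They apply to a proportion of infants with hyperthermia if the infant has no other graded fever. They apply to a proportion of infants with any adverse event only if the infant has no other adverse event of any kind. Table 3 also counts a haematocrit below 34%, a triglyceride of 150 to 250 mg/dL and a single glucose above 180 mg/dL. Monitoring runs from the start of study lipid until 7 days after leaving the study, with lipid lasting up to 84 days. The documents give no frequency for isolated high fevers, so no expected number can be stated.

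**Oliguria.** Urine output from 0 to 1.50 mL/kg/h in steps of 0.01 (151 values):

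| Output (mL/kg/h) | Number of values | Grades met | Highest grade |
|---|---|---|---|
| 0.00 to 0.29 | 30 | 1, 3 and 4 | 4 |
| 0.30 to 0.49 | 20 | 1 and 3 | 3 |
| 0.50 to 0.99 | 50 | 1 and 2 | 2 |
| exactly 1.00 | 1 | 2 only | 2 |
| 1.01 to 1.50 | 50 | none | none |

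No value meets Grade 1 alone. If the highest grade met is recorded, Grade 1 is empty.

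Nested cut-points are not the cause. The anaemia row is also nested (haematocrit below 34, 28, 24 and 20%), and the same rule leaves all four of its grades in use: 28 to below 34, 24 to below 28, 20 to below 24, and below 20. The oliguria row fails because Grade 2 covers the whole part of Grade 1 that lies above Grade 3.

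Every output up to and including 1.00 meets at least one grade. The count of infants with oliguria is therefore the same under any grading rule.

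**The case against.** The strongest defence of the fever row is that Table 3 is not the only source of definitions. The protocol says adverse events are defined by CTCAE version 4.0 and that the table lists some specific events. The first row of the table is a general severity definition, under which a high fever that altered care could be graded. This does not close the gap. Hyperthermia has its own row, and the restriction on laboratory and vital sign changes says they count only on the specific table criteria. At most, the two statements pull in different directions.

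A second defence is that few infants would be affected. A second consecutive reading of 38.5 °C or above reaches Grade 3, and a need for more IV fluid can be read as reaching Grade 4. That stands, and it limits the point to isolated readings without that need. A reader might infer that every temperature above 39.0 °C is lost; the table does not support that.

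On oliguria, a reader might infer three things that the documents do not bear out:

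- *The overlap distorts adverse event rates.* It does not: any output below 1.0 mL/kg/h is an adverse event on every reading, and the plan describes no analysis by grade. Serious events are defined by outcome and not by this boundary.
- *Mild oliguria is recorded as moderate.* That presumes a correct mild band within 0.5 to 1.0, and the documents define none.
- *An output below 0.3 could be called mild.* That needs a lowest-match rule, which would make the anaemia row meaningless.

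Nor does Grade 1 contain the whole of Grade 2, because exactly 1.0 is Grade 2 only.

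**Conclusion.** The hyperthermia gap is real in the current text. As written, an isolated axillary reading above 39.0 °C without a need for increased IV fluid is not an adverse event, while an isolated reading of 38.0 to 39.0 °C is. The effect is at most 4 points per affected infant on a hyperthermia-specific proportion in an arm of 25, or about 8 in an arm of 12. An any-event proportion changes only for an infant with no other adverse event. This rests on taking the word only in the adverse-event section at face value, and on the fluid clause being either absent or not met.

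The oliguria overlap is also real but smaller. It leaves Grade 1 with no values under a highest-grade reading, which the anaemia row needs in order to work. It changes recorded grades and no planned count, so the 4- and 8-point figures do not apply to it.

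It would be too much to conclude that the safety comparison is materially biased. The documents give no event frequency and no reason to expect the gap to fall more on one arm. The cholestasis outcome is untouched. This is a minor correction, worth making because it is nearly free and the rule feeds objective 2.h and the monitoring committee's review.

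**What to change.** 1. In the hyperthermia row, make the single-reading Grade 2 band open-ended: 38.5 °C or higher on a single measurement. No higher single reading is then ungraded, and Grades 3 and 4 stay as they are.
2. Add one sentence to the adverse-event section saying that when a value meets several grades, the highest is recorded. This also settles the shared boundary at 38.5 °C and the nested anaemia row.
3. Have the sponsor reconcile the oliguria Grade 1 and Grade 2 cut-points so that they do not overlap, or delete Grade 1. Where the boundary lies is the sponsor's choice.

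The cost is two table cells and one sentence. These are changes to event classification only; sample size, study procedures and the data collected stay the same. If infants have already been enrolled, isolated readings above 39.0 °C should be looked for in the records and classified under the amended row, in both arms alike.
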